7.4 Summary Tables/Listings

Summary tables, participant listings, graphs and any supportive SAS output will include a "footer" of explanatory notes that will indicate, when applicable:

- date of data extraction

- date and time of output generation
- SAS program name that generates the output

Null summary tables will be presented with a note stating that “No Participants Met Criteria.”

Individual participant listings will be provided as support for summary tables and serve as a data source substitute when a summary table is deemed either inappropriate or unnecessary. All participant listings will be sorted by participant number. When applicable, the participant listings will include the visit date, and days relative to the start of first treatment.

7.5 Pharmacokinetic Data (if available)

All Day 1 pre-dose concentration values below the limit of quantification (BLOQ) will be treated as zero. Due to the small sample size in this sub-study and the anticipated low plasma concentration, for the purpose of mathematical operation, instead of treating post-dose concentration BLOQ values as zero for statistical analyses, these values will be set as “missing”. However, for the display of the order statistics (minimum, first quartile [Q1], median, third quartile [Q3], maximum), if at least 1 reading is BLOQ for the time point, then the minimum value will be displayed as “BLOQ”. If more than 50% of the readings are BLOQ for the time point, then the minimum and median values will be displayed as “BLOQ”. If all values are BLOQ for the time point, then all statistics will be displayed as “BLOQ”.

BLOQ values will be presented as “BLOQ” in the concentration data listing.

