3.1.5 Pharmacokinetic Measure (if applicable)

A subset of 6 participants from each treatment group will participate in a PK study to collect blood samples on the morning of Day 1 and Day 28 at pre-dose, at 0.5, 1 hour post-dose. On Day 56, a single blood sample will be collected. Plasma drug concentrations will be measured using a validated liquid

chromatography, tandem mass spectrometry assay, with a target lower limit of quantitation of 0.020 ng/mL.

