4.6 Pharmacokinetic Endpoints (if available)

Data on plasma drug concentrations, if available, will be collected for those participating in the sub-study. Pharmacokinetic endpoints include:

- Individual and mean concentration and standard deviation for Day 1, Day 28, and Day 56
- Partial Area Under the Curve (AUC_{0-1h}) on Day 1 and Day 28

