6 STATISTICAL METHODS

All data processing, summarization, and analyses will be performed using SAS® Version 9.4 or higher.

Unless otherwise specified, for continuous variables, descriptive statistics will include the number of participants/eyes (n), mean, standard deviation, median, minimum and maximum values. Categorical variables will be summarized using frequency and percentages.

Unless, otherwise stated, missing data will be handled as is, except when the aforementioned dates are required for calculations, the partial dates will have either '01' or 'Jan' imputed with an exception for dates related to AEs where the date closest to the last event (screening, first dose, last dose, etc.) should be used rather than arbitrary '01' of that month.

All efficacy data will be summarized by treatment group and time point using appropriate descriptive statistics. Summaries will be presented for both the mITT and PP populations. Due to the small number of participants that are expected to be enrolled at each center, all summaries and analyses will be performed using data pooled across centers.

Baseline results will be those recorded prior to dosing. In cases where more than one pre-dose observation has been recorded, the **last recording** will be identified as the baseline result.

Study days will be numbered relative to the date of the first dosing. The start of study (Day 1) will be defined as the date on which a participant takes the first dose of any study medication, as recorded on the CRF. Relative to study start, days will be numbered ...-2, -1, 1, 2, ... with Day - 1 being the day prior to the start of study medication (Pre-Dose).

Recorded data will be assigned to evaluation/assessment windows. If more than one clinical evaluation is made within a window for a particular visit, the record with the date closest to the targeted window will be used except for AEs where the **worst assessment** will be used.

Visit windows and analytical windows are defined as follow:

Visit	Targeted Window	Analytical Window
Pre-dose (Screening)	Day -14 to Day -1	Day -18 to Day -1
Visit 1 (First dosing date)	Day 1	Day 1
Visit 2 (optional)	Day 7 (± 3 day)	Day 2 to Day 16
Visit 3 (End of treatment visit)	Day 28 (± 3 days)	Day 17 to 3 days after the last dose and up to Day 42
Visit 4	Day 56 (± 5 days)	Day 43 to Day 70
Visit 5 (End of study visit)	Day 84 (± 5 days)	Day 71 to End of Study

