6.7 Pharmacokinetic Analyses (if data available)

Pharmacokinetic analysis, if applicable, will be based on the PK sub-population using a model-independent approach.

Drug plasma concentration data will be summarized for each dose by descriptive statistics using SAS®. AUC_{0-1h} will be estimated using linear trapezoidal method.

Individual and mean concentration at each time point, C_{max} , T_{max} , and AUC_{0-1h} , where applicable, will be presented by treatment group for Day 1 and Day 28. On Day 56 individual and mean \pm SD will be presented.

Individual and mean concentration-time curves will be presented for Day 1, and Day 28 to illustrate the dynamic change of plasma concentration from hour 0 to 1.

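### Where some but not all post-dose concentrations at a time point are BLOQ, SAP 7.5 averages only the quantifiable samples, so the reported group mean is too high

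*SAP*

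**What the plan says.** The pharmacokinetic endpoints in SAP 4.6 are "Individual and mean concentration and standard deviation for Day 1, Day 28, and Day 56". SAP 6.7 plans "Individual and mean concentration at each time point" by treatment group for Days 1 and 28, with a mean and SD on Day 56. SAP 3.1.5 sets the size and the assay: "A subset of 6 participants from each treatment group will participate in a PK study", "with a target lower limit of quantitation of 0.020 ng/mL". Protocol 8.2 gives 6 per group as a minimum.

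SAP 7.5 sets the BLOQ rule. Day 1 pre-dose BLOQ values count as zero. For later values, citing the small sub-study and the low concentrations expected, it says that "instead of treating post-dose concentration BLOQ values as zero for statistical analyses, these values will be set as" missing. Three display rules follow:

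- If at least one value at a time point is BLOQ, the minimum is shown as BLOQ.
- For a majority: "If more than 50% of the readings are BLOQ for the time point, then the minimum and median values will be displayed as" BLOQ.
- If every value is BLOQ, all statistics are shown as BLOQ.

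Only the third rule reaches the mean. No rule covers the mean in a row with some but not all values BLOQ (a mixed row below). SAP 6 adds the general convention: "descriptive statistics will include the number of participants/eyes (n), mean, standard deviation, median, minimum and maximum values".

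**The concern.** A BLOQ result carries information: the concentration is somewhere between zero and the LLOQ. Setting it to missing removes the lowest values from the average and leaves the highest. SAP 7.5 itself expects low concentrations, which is the setting in which mixed rows can arise. With 4 of 6 values BLOQ, the table would show a median of BLOQ beside a numeric mean built from two samples at or above the LLOQ.

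Plasma concentration is a stated objective in protocol section 3, and protocol 2.1 says that human pharmacokinetics after topical dosing have not been studied. At stake is whether the printed group mean describes the group, or only those members with measurable drug.

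**Working it through.** The documents give no figure to reproduce here; the check is algebra on the stated rule.

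**Inputs.** n = 6 per arm (SAP 3.1.5); L = LLOQ = 0.020 ng/mL, a target value (SAP 3.1.5); k = number BLOQ, with 0 < k < n; mQ = mean of the quantifiable values, so mQ ≥ L; mB = mean of the true values behind the BLOQ results, so 0 ≤ mB < L. The documents give no BLOQ rate and no expected concentration, so mQ below is an assumption.

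**Direction.**
- Mean reported under SAP 7.5: mQ.
- Mean of all samples: [(n − k)·mQ + k·mB] / n.
- Difference: (k/n)(mQ − mB).

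Because mQ ≥ L > mB, the difference is positive in every mixed row, for any distribution and any LLOQ.

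**Largest ratio.** The ratio of reported to all-sample mean is largest when mB = 0, where it equals n/(n − k). For n = 6 this is 6/5 = 1.2, 6/4 = 1.5, 6/3 = 2, 6/2 = 3 and 6/1 = 6 for k = 1 to 5. These limits do not depend on L.

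**Worked example.** Assume mQ = 0.030 ng/mL, which is 1.5 × L. The lower all-sample mean is (6 − k)(0.030)/6; the upper limit is [(6 − k)(0.030) + k(0.020)]/6.

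| BLOQ of 6 | Reported mean | All-sample mean, BLOQ = 0 | All-sample mean, BLOQ at LLOQ | Overstated by a factor of |
|---|---|---|---|---|
| 1 | 0.030 | 0.0250 | 0.0283 | 1.06 to 1.2 |
| 2 | 0.030 | 0.0200 | 0.0267 | 1.125 to 1.5 |
| 3 | 0.030 | 0.0150 | 0.0250 | 1.2 to 2.0 |
| 4 | 0.030 | 0.0100 | 0.0233 | 1.29 to 3.0 |
| 5 | 0.030 | 0.0050 | 0.0217 | 1.38 to 6.0 |

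**Numerical check.** Rows of 6 were simulated under an assumed lognormal distribution with log-SD 0.6. The quantifiable-only mean exceeded the all-sample mean in all 205,910 mixed rows. The average factor was 2.05, 1.48 and 1.19 for assumed medians of 0.01, 0.02 and 0.04 ng/mL.

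**Check of the remedy.** Setting BLOQ to zero gives (n − k)·mQ/n, which cannot exceed the all-sample mean. Setting BLOQ to L gives U = [(n − k)·mQ + k·L]/n, which is above it. Since L ≤ mQ, U ≤ mQ. So the all-sample mean lies below U, and U is no greater than the SAP mean: the LLOQ-substituted mean is never further from the all-sample mean than the SAP mean is. The bounds are k·L/n apart, for example 3 × 0.020/6 = 0.010 ng/mL at k = 3. No distribution is assumed.

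**The case against.** The rule is a reasoned choice. SAP 7.5 names zero as the alternative and declines it, and every simple BLOQ rule is a convention with some bias. This stands as an argument against imposing another single substitution. It does not make the quantifiable-only mean a group mean.

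The omission is also well disclosed. Every mixed row shows a minimum of BLOQ and a reduced n, the median shows BLOQ above 50%, and the individual values are presented. This lowers the weight of the point. A reader is warned, but still cannot read the group mean from the summary table.

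Three stronger readings are tempting, and the documents do not support them.

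- *The trial's safety case is affected.* The error overstates exposure, which is conservative for safety. The low-risk argument in protocol 2.2 and 2.3.1 rests on animal AUC and administered dose. No test, dose-selection rule or stopping rule uses these means.
- *Half the LLOQ must replace the SAP rule.* Take a lognormal with 50% BLOQ, so that the LLOQ is the median, and σ² = ln(1 + CV²). The SAP mean is then 2Φ(σ) of the true mean, and the half-LLOQ mean is Φ(σ) + ¼·exp(−σ²/2) of it. At CV 15% these are 1.12 and 0.81, so the SAP rule is closer. At CV 50% they are 1.36 and 0.905, so half-LLOQ is closer. The documents give no CV, and half-LLOQ understates exposure in both cases.
- *The mean should be withheld when most values are BLOQ.* That would remove quantities that SAP 4.6 lists as endpoints.

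Finally, n = 6 is a planning figure and the sub-study is conditional on data being available, so the ratios are illustrative. For another n, the limit is n/(n − k).

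**Conclusion.** The point holds, as a minor one. In any mixed row, SAP 7.5 yields a mean that is too high by (k/n)(mQ − mB) and cannot fall below the LLOQ. The direction follows from the definition of BLOQ alone. The size, at most 1.2 to 6 times for 1 to 5 BLOQ of 6, depends on a BLOQ share and concentrations that the documents do not give. There is no bias when no value is BLOQ, and all-BLOQ rows are already displayed correctly.

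A reader might infer that the pharmacokinetic results will be inflated. The documents support only the conditional statement, because how often mixed rows will occur is unknown. The consequence is an inaccurate summary of a descriptive objective in those rows, with no effect on any efficacy or safety conclusion.

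**What to change.** Amend SAP 7.5 for the active arms:

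- In mixed rows, do not present the quantifiable-only mean as the group mean.
- Print the number and percent BLOQ.
- Report the mean with post-dose BLOQ values set to zero and again with them set to the validated assay LLOQ, described as lower and upper bounds that contain the all-sample mean.
- If the quantifiable-only mean is kept as well, label it as the mean of quantifiable samples only, and state which values any SD comes from.
- A half-LLOQ mean may be added, footnoted as a convention.

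The present displays of minimum, median and all-BLOQ rows can stay.

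The cost is SAP wording and some programming before the first database lock, with no new samples. The downside is a slightly busier table and a range instead of one mean in mixed rows.

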8 INTERIM ANALYSES

No interim analysis for efficacy is planned for this study.

Two database locks are scheduled for this study. The first database lock will occur after all participants completed the Day 28 visit for the primary efficacy analysis (including grading by the central reading center), localized pterygium conjunctival hyperemia, PK analysis (if applicable), and summary of safety data gathered up-to-date. The final lock will occur at study completion (Day 84) for longer term assessment of safety, tolerability, treatment effect, and plasma concentrations monitoring of AG-86893 (if applicable). Eligibility for analysis will be determined prior to each database lock.

9 QUALITY CONTROL AND VALIDATION

Derived datasets will be independently reprogrammed by a second programmer. The separate datasets produced by the two programmers must match 100%.

Tables will be independently reprogrammed by a second programmer for numeric results. Statisticians will be involved in the process of validating tables that include inferential statistical results.

Figures will be checked for consistency against corresponding tables and listings, or independently reprogrammed if there are no corresponding tables or listings.

Please refer to the following Trial Runners Standard Operating Procedures for details on related activities/procedures.

- CN-SOP-6001 Preparation & Communications of Key Results
- CN-SOP-6002 SAP Development and Maintenance
- CN-SOP-6003 Analysis Datasets Development
- CN-SOP-6301 Running of Statistical Programs
- CN-SOP-8001 SAS Programming Standards
- CN-SOP-8002 SAS Requirements Specifications
- CN-SOP-8003 Program Design-Implementation
- CN-SOP-8004 Program Verification and Validation
- CN-SOP-8005 Running of SAS Programs

APPENDIX 1 GLOSSARY OF ABBREVIATIONS

AE	adverse event
ALT	alanine aminotransferase
AST	aspartate aminotransferase
AUC	area under the plasma concentration-time curve
AS-OCT	anterior-segment optical coherence tomography
BCVA	best-corrected visual acuity
BID	twice daily
CFR	Code of Federal Regulations
CI	confidence interval
C _{max}	maximum plasma concentration
CONSORT	consolidated Standards of Reporting Trials
ECG	electrocardiogram
eCRF	electronic Case Report Form
EDTA	ethylenediaminetetraacetic acid
FGF-2	fibroblast growth factor-2
FGFR	fibroblast growth factor receptor
GCP	Good Clinical Practice
GLP	Good Laboratory Practice
HIPAA	Health Insurance Portability and Accountability Act Standards for Privacy of Individually Identifiable Health Information
HPMC	hypromellose; hydroxypropyl methylcellulose
HREC	Human Research Ethics Committee
IC ₅₀	half-maximal inhibitory concentration
ICF	informed consent form
ICH	International Conference on Harmonisation
IEC	International Ethics Committee
IOP	intraocular pressure
IRB	Institutional Review Board
IVRS	Interactive Voice Response System
IWRS	Interactive Web Response System
LDPE	low-density polyethylene
MedDRA	Medical Dictionary for Regulatory Activities
mITT	modified intent-to-treat
MMPs	matrix metalloproteinases

MOP	Manual of Procedures
NOAEL	no-observed-adverse-effect-level
PDGFR	platelet-derived growth factor
PDGFR β	platelet-derived growth factor receptor β
PK	pharmacokinetic(s)
PP	per-protocol
RBC	red blood cell
RLD	reference listed drug
QC	quality control
QID	4 times daily
SAE	serious adverse event
SAP	Statistical Analysis Plan
SD	standard deviation
SUSAR	suspected unexpected serious adverse reaction
T _{1/2}	half-life
T _{max}	time to reach maximum plasma concentration
TID	3 times daily
ULN	upper limit of normal
US	United States
VEGF	vascular endothelial growth factor
VEGFR	vascular endothelial growth factor receptor
WBC	white blood cell
YAG	yttrium aluminium garnet

APPENDIX 2 SAMPLE SAS CODE FRAGMENT

For estimation of main treatment effect:

SAS pseudo code for main treatment effect and LS mean estimation:

```
proc mixed data=xxx;  
  where mitt='Y'; *select the designated analysis population here (e.g.,  
  itt, pp);  
  class TREAT; *include other categorical covariants;  
  model CHANGE_OVERALL = TREAT/ddfm=statterth; *if any, include covariants  
  and interaction terms;  
  lsmeans TREAT/pdiff cl adjdfe=row adjust=bon;  
  (ods output statements)  
run;
```

SAS pseudo code for estimation of proportions and 95% CI, and the difference in proportions:

```
proc freq data=xxx;  
  tables VAR1 * VAR2/ alpha = 0.05 riskdiff (CL = MN);  
  * Miettinen and Nurminen inverted score test;  
  (ods statements)  
run;
```
